9.7.3 Analyses of Health Economic Endpoints

Subject incidence rate of following endpoints: TEAEs that resulted in hospitalizations, TEAEs that resulted in surgeries, TEAEs that resulted in use of concomitant medications, TEAEs that resulted in use of device/procedure intervention will be summarized and accompanied by 2-sided 95% exact binomial confidence intervals (Clopper and Pearson, 1934).

9.7.4 Analyses of Biomarker Endpoints

Not applicable.

10. Changes From Protocol-specified Analyses

For estimation of secondary objective on healthcare resource utilization, the endpoints are updated to treatment-related TEAEs instead of the TEAEs in consistency with the objective.

CAD Costion	Iludete
SAP Section	
Section 2.1	a) The wording of below primary and secondary endpoints
	from protocol are modified in the SAP to clarify what
	endpoints are exactly evaluated at the subject level:
	Primary endpoint: Incidence of grade 3 and/or 4 CRS,
	NT or any adverse event (AE) requiring hospitalization
	(SAE) during MDMP
	Secondary endpoint: Overall incidence and severity of
	treatment-emergent adverse events (TEAE) and adverse
	events of interest in particular CRS and NT
	b) For estimation of secondary objective on healthcare
	resource utilization, the endpoints are updated to include
	'treatment-related TEAEs' instead of the 'TEAEs' in
	consistency with the objective.
Section 8.3	Subject replacement rule for analysis is updated to exclude the
	below criterion from protocol. Since the replacement rule is
	defined for analysis, an additional text on replacement status
	applicability for internal data analysis also excluded.
	Text from protocol section 4.2.1 excluded from SAP section
	8.3:
	Subjects are removed from treatment with IP due to disease
	progression.
	Replacement status is only applicable for internal data
	analysis.

11. Literature Citations / References

12. Prioritization of Analyses

Not applicable

13. Data Not Covered by This Plan

Not applicable.

14. Appendices

Appendix A Reference Values/Toxicity Graders Table 14-A. Summary of Potential Hy's Law Cases (Safety Analysis Set)

	Blinatumomab
	(N = XXX)
Pre-infusion - n/N1(%)	
ALT or AST >3xULN	xx/xxx (xx.x)
TBL ≥2xULN	xx/xxx (xx.x)
ALP <2xULN	xx/xxx (xx.x)
(ALT or AST) >3xULN & TBL ≥2xULN & ALP <2XULN any day	xx/xxx (xx.x)
(ALT or AST) >3xULN & TBL ≥2xULN & ALP <2XULN within one day	xx/xxx (xx.x)
On-study - n/N1(%)	
ALT or AST >3xULN	xx/xxx (xx.x)
TBL ≥2xULN	xx/xxx (xx.x)
ALP <2xULN	xx/xxx (xx.x)
(ALT or AST) >3xULN & TBL ≥2xULN & ALP <2XULN any day	xx/xxx (xx.x)
(ALT or AST) >3xULN & TBL ≥2xULN & ALP <2XULN within one day	xx/xxx (xx.x)
	Page 1 of 1

n=number of subjects who met criteria

N1= number of subjects with available data

ALP=Alkaline Phosphatase; ALT=Alanine Aminotransferase; AST=Aspartate Aminotransferase; TBL=Total Bilirubin.

Appendix B Clinical Outcome Assessment Forms/Instruments Table 14-B-1. EORTC Quality of Life Questionnaire

EORTC QLQ-C30 (version 3)

We are interested in some things about you and your health. Please answer all of the questions yourself by circling the number that best applies to you. There are no "right" or "wrong" answers. The information that you provide will remain strictly confidential.

Ple Yo To	ase fill in your initials: ur birthdate (Day, Month, Year): day's date (Day, Month, Year): 31				
_		Not at All	A Little	Quite a Bit	Very Much
1.	Do you have any trouble doing strenuous activities, like carrying a heavy shopping bag or a suitcase?	1	2	3	4
2.	Do you have any trouble taking a long walk?	1	2	3	4
3.	Do you have any trouble taking a short walk outside of the house?	1	2	3	4
4.	Do you need to stay in bed or a chair during the day?	1	2	3	4
5.	Do you need help with eating, dressing, washing yourself or using the toilet?	1	2	3	4
Dı	uring the past week:	Not at All	A Little	Quite a Bit	Very Much
6.	Were you limited in doing either your work or other daily activities?	1	2	3	4
7.	Were you limited in pursuing your hobbies or other leisure time activities?	1	2	3	4
8.	Were you short of breath?	1	2	3	4
9.	Have you had pain?	1	2	3	4
10.	Did you need to rest?	1	2	3	4
11.	Have you had trouble sleeping?	1	2	3	4
12.	Have you felt weak?	1	2	3	4
13.	Have you lacked appetite?	1	2	3	4
14.	Have you felt nauseated?	1	2	3	4
15.	Have you vomited?	1	2	3	4
16.	Have you been constipated?	1	2	3	4

Please go on to the next page

During the past week:	Not at All	A Little	Quite a Bit	Very Much
17. Have you had diamhea?	1	2	3	4
18. Were you tired?	1	2	3	4
19. Did pain interfere with your daily activities?	1	2	3	4
20. Have you had difficulty in concentrating on things, like reading a newspaper or watching television?	1	2	3	4
21. Did you feel tense?	1	2	3	4
22. Did you worry?	1	2	3	4
23. Did you feel initable?	1	2	3	4
24. Did you feel depressed?	1	2	3	4
25. Have you had difficulty remembering things?	1	2	3	4
26. Has your physical condition or medical treatment interfered with your family life?	1	2	3	4
27. Has your physical condition or medical treatment interfered with your social activities?	1	2	3	4
28. Has your physical condition or medical treatment caused you financial difficulties?	1	2	3	4

For the following questions please circle the number between 1 and 7 that best applies to you

	. How would you rate your overall health during the past week?								
7	6	5	4	3	2	1			
Excellent						ry poor	Ve		

30. How would you rate your overall quality of life during the past week?

1	2	3	4	5	6	7
Very poor						Excellent

© Copyright 1995 EORTC Quality of Life Group. All rights reserved. Version 3.0

Scale/Item Name (PARAM)	Abbreviation	Number of Items	Item Range*	Item numbers	Minimum # of non-missing items needed
Global health status/					
Global health status/QoL	QL2	2	6	29, 30	1
Functional scales					
Physical functioning	PF2	5	3	1 to 5	3
Role functioning	RF2	2	3	6, 7	1
Emotional functioning	EF	4	3	21 to 24	2
Cognitive functioning	CF	2	3	20, 25	1
Social functioning	SF	2	3	26, 27	1
Symptom scales					
Fatigue	FA	3	3	10, 12, 18	2
Nausea and vomiting	NV	2	3	14, 15	1
Pain	PA	2	3	9, 19	1
Symptom Single item	IS				
Dyspnoea	DY	1	3	8	N/A
Insomnia	SL	1	3	11	N/A
Appetite loss	AP	1	3	13	N/A
Constipation	СО	1	3	16	N/A
Diarrhoea	DI	1	3	17	N/A
Financial difficulties	FI	1	3	28	N/A

Table 14-B-2. Correspondence of the EORTC QLQ-C30 questions to the scale

*Item range is the difference between the possible maximum and the minimum response to individual items

Appendix C Eastern Cooperative Oncology Group Performance Status (ECOG PS) Scale

ECOG PS Scale						
Grade	Descriptions					
0	Fully active, able to carry on all pre-disease performance without restriction.					
1	Restricted in physically strenuous activity, but ambulatory and able to carry out work of a light or sedentary nature (eg, light housework, office work).					
2	Ambulatory and capable of all selfcare, but unable to carry out any work activities. Up and about more than 50% of waking hours.					
3	Capable of only limited selfcare, confined to bed or chair more than 50% of waking hours.					
4	Completely disabled. Cannot carry on any selfcare. Totally confined to bed or chair.					
5	Dead					

Source: Oken et al, 1982.

Appendix D Handling of Dates, Incomplete Dates and Missing Dates for Adverse Events and Concomitant Medications The following data will be imputed using the following algorithm:

- Adverse Events
- Concomitant Medications

		Stop Date							
		Complete: yyyymmdd		Partial: yyyymm		Partial: уууу			
Start Date		< 1 st dose	≥ 1 st dose	< 1 st dose yyyymm	≥ 1 st dose yyyymm	< 1 st dose yyyy	≥ 1 st dose yyyy	missing	
Partial: yyyymm	= 1st dose yyyymm	2	1	2	1	n/a	1	1	
	≠ 1 st dose yyyymm		2		2	2	2	2	
Partial: yyyy	= 1 st dose yyyy	3	1	3	1	n/a	1	1	
	≠ 1 st dose yyyy		3		3	3	3	3	
Missing		4	1	4	1	4	1	1	

Table 14-D-1. Imputation Rules for Partial or Missing Start Dates

1 = Impute the date of first dose

2 = Impute the first of the month

3 = Impute January 1 of the year

4 = Impute January 1 of the stop year

Note: If the start date imputation leads to a start date that is after the stop date, then do not impute the start date.

Imputation rules for partial or missing stop dates:

Initial imputation

- For partial stop date mmyyyy, impute the last of the month.
- For partial stop date yyyy, impute December 31 of the year.
- For completely missing stop date, do not impute.
- If the stop date imputation leads to a stop date that is after the death date, then impute the stop date as the death date.
- If the stop date imputation leads to a stop date that is before the start date, then there is a data error and do not impute the stop date. (ie. set the stop date as missing).

Imputation rules for partial or missing death dates:

- If death year and month are available but day is missing:
- If mmyyyy for last contact date = mmyyyy for death date, set death date to the day after the last contact date.
- If mmyyyy for last contact date < mmyyyy for death date, set death date to the first day of the death month.
- If mmyyyy for last contact date > mmyyyy for death date, data error and do not impute.
- If both month and day are missing for death date or a death date is totally missing, do not impute.

Note that the last contact date refers to the last contact (i.e. a visit or an assessment) with patient instead of family members. Last contact date would be derived from the latest patient visit/assessment date.

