4.2 Subgroups

Due to small sample size, subgroup analysis will not be performed.

5. Definitions

Age at Enrollment:

Subject age at enrollment will be collected in years in the clinical database.

Adverse Event During the MDMP

Adverse event during the MDMP is defined as an adverse event that started within 72 hours after the first dose of blinatumomab in cycle 1 and within 48 hours after the first dose of blinatumomab in cycle 2.

For adverse events with missing start time, the adverse event during the MDMP is defined as an adverse event that started within 3 days after the first dose date of blinatumomab in cycle 1 and within 2 days after the first dose date of blinatumomab in cycle 2.

Baseline

The baseline value will be defined as the value measured on day 1 of the first cycle before start of the first infusion of blinatumomab. If a cycle 1 day 1 value is not available, the latest value before the day 1 of the start of blinatumomab infusion may be used.

Cumulative Dose of Blinatumomab

The cumulative dose in μg is defined as the following with summation over infusions:

 \sum Duration of infusion [days] for each dose received × dose received [μ g/day].

Cumulative dose will be calculated within a cycle and across all cycles.

Duration of Therapy

For each infusion episode within a cycle, the duration of exposure will be calculated by subtracting the start date and time from the stop date and time. If either a start or stop time is missing, only the date portion will be used in calculating the duration of a specific

infusion. For each cycle, the duration will be the sum of the individual infusion durations within that cycle. For the entire study, the duration will be the sum of the durations across cycles. The duration will be rounded to the nearest day.

End of Study

The end of study date is defined as the date when the last subject across all sites is assessed or receives an intervention for evaluation in the study (i.e. last subject last visit).

End of Study Visit

The end of study visit will occur 30 days (\Box 3 days) after the last dose of blinatumomab is given. The end of study visit will occur after cycle 3 or 4 for subjects who chose these optional cycles. End of study visit date for each subject will be recorded on the End of Study CRF page.

Enrollment Date

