8.3 Handling of Missing and Incomplete Data

In general, missing data will be treated as missing, unless stated otherwise. Missing response for questions in EORTC QLQ-C30 PRO will be imputed as defined in section 5 of this SAP.

The handling of incomplete and partial dates for adverse events and concomitant medications are described in Appendix D.

Subjects will be replaced for analysis if the outpatient monitoring during blinatumomab infusion is not established.

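### SAP Appendix D's imputed start dates are not fit to decide MDMP membership: some incompletely dated AEs enter the cycle 1 window by rule, and month-only cycle 2 events usually drop out.

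*SAP*

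**What the plan says.** SAP Section 8.3 sends incomplete AE dates to one place: "The handling of incomplete and partial dates for adverse events and concomitant medications are described in Appendix D". It makes no exception for the primary endpoint.

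Table 14-D-1 in SAP Appendix D works as follows:

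- **Code 1**, "1 = Impute the date of first dose": the start is known only to the first-dose month, known only to the first-dose year, or fully missing, and the stop date is on or after first dose or is missing.
- **Code 2**, "2 = Impute the first of the month": the start is known to some other month, or to the first-dose month when the stop precedes first dose.
- **Code 3**, "3 = Impute January 1 of the year": the start is known only to another year, or to the first-dose year when the stop precedes first dose.
- **Code 4**, "4 = Impute January 1 of the stop year": the start is fully missing and the stop precedes first dose.
- **Note**: "If the start date imputation leads to a start date that is after the stop date, then do not impute the start date".

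SAP Section 5 defines an MDMP adverse event by hours from the first dose of the cycle. Without a start time it uses dates: the event counts if it "started within 3 days after the first dose date of blinatumomab in cycle 1 and within 2 days after the first dose date" of cycle 2. No code in Appendix D uses the cycle 2 first-dose date as a target.

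**The concern.** Moving an uncertain start to first dose is a familiar, cautious convention for deciding whether an AE is treatment-emergent. Here it is hardly needed for that, because SAP Section 5 settles treatment emergence from an eCRF question on whether the event began before first dose. The imputed date matters more for MDMP membership, and for the time to onset and duration of selected events of interest (SAP Section 9.6.2). For these a shift of a few days changes the answer.

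Two errors of opposite sign are possible. A hospitalised AE, or a grade 3/4 CRS or NT event, with a code 1 date becomes a cycle 1 primary event even if it began weeks later. A genuine cycle 2 MDMP event recorded to the month only is dated to the 1st and usually leaves the endpoint. In addition, neither Appendix D nor the MDMP definition consults the pre-dose question. SAEs are collected from consent, so a month-only SAE that began before dosing in the first-dose month and was still ongoing would also be dated to first dose.

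**Working it through.** **Inputs.** N = 45, event probability 38% and expected upper limit 53.5% (SAP Section 3.2). Two-sided 95% Clopper-Pearson interval (SAP Section 9.6.1). Cycle length 6 weeks, with the treatment-free interval extendable by up to 7 days (protocol synopsis), so C2D1 falls 42 to 49 days after C1D1. Imputation codes from Table 14-D-1 and date windows from SAP Section 5. Assumption throughout: the stop date is missing or late enough not to alter the code.

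**1. The plan's own figure.** 45 × 0.38 = 17.1, so about 17 events. Clopper-Pearson for 17/45 gives 23.8% to 53.5%, and the upper limit averaged over Binomial(45, 0.38) is 53.5%. The stated figure is reproduced.

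**2. Code 1 and cycle 1.** The imputed date is day 0, which is inside the cycle 1 window on any reading of the date rule, so 100% of code 1 dates count. The share truly inside depends on the onset pattern, which the documents do not give. For a month-only start, let L be the days left in the month including the dosing day, and take days 0 to 3 as the window.

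- Uniform onset over the rest of the month: share = min(4, L)/L. Over 365 possible first-dose dates the median is 25% and the mean 38%. Dosing on the 5th of a 30-day month gives 4/26 = 15%.
- Onset declining exponentially with mean m days: share = (1 − e^(−min(4,L)/m)) / (1 − e^(−L/m)). The median is 74% for m = 3, 57% for m = 5, 48% for m = 7 and 36% for m = 14.

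**3. Month-only cycle 2 events.** With a gap of 42 to 49 days, C2D1 is never in the first-dose month, so code 2 always applies. Take event days C2D1 to C2D1+2. The 1st of the event's month lies in the window in only these cases:

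| C2D1 falls on | Event days kept |
|---|---|
| the 1st | 3 |
| the last day of a month | 2 |
| the day before that | 1 |

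That is 6 kept of 3 × 30.4 = 91.3 event days per average month: 6/91.3 = 6.6%. If the window is read as two calendar days only, it is (2 + 1)/(2 × 30.4) = 4.9%. Enumerating every first-dose date over four years gives the same figures.

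**4. Other incomplete cycle 2 starts.** From the same enumeration:

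| What is known of the start | Kept in cycle 2 | Counted under cycle 1 | Lost |
|---|---|---|---|
| Month and year | 5 to 7% | 0% | 93 to 95% |
| Year only | about 0.5% | 87 to 89% | 10 to 13% |
| Nothing | 0% | 100% | 0% |

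The year-only losses arise when the year changes between the cycles.

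**5. Example.** First dose 6 June, C2D1 18 July, event 19 July. Recorded as July, the start becomes 1 July and is not counted. Recorded to the year only, it becomes 6 June and is counted. The more informative record is the one that loses the event.

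**6. Effect of one subject.** 1/45 = 2.2 points.

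| Events | Rate | 95% interval |
|---|---|---|
| 16/45 | 35.6% | 21.9% to 51.2% |
| 17/45 | 37.8% | 23.8% to 53.5% |
| 18/45 | 40.0% | 25.7% to 55.7% |

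**The case against.** The strongest reply is that this will rarely happen. Onset date is a mandatory AE attribute (protocol Appendix 4), and the SAE contingency form makes the start date mandatory and asks for admission and discharge dates. SAEs are reported within 24 hours, source data are verified, and SAP Section 8.1 sends outstanding data issues for resolution before lock. True MDMP events occur under continuous monitoring with video calls at least every 12 hours, so they are the events least likely to lack a day. All of this stands and limits the practical weight. It does not stop the rule acting on a date that stays unresolved, and resolution before lock does not by itself protect the interim reviews.

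Second, the Section 5 fallback ("For adverse events with missing start time, the adverse event during the MDMP is defined as an adverse event that started within 3 days") can be read as covering a known date with no time, so the link to Appendix D is inferred. That is fair. But Section 8.3 sends AE dates to Appendix D without exception, and nothing bars the imputed date from the flag.

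Third, uniform onset is an assumption, and the protocol points to early onset: most AEs fell within the first few weeks of cycle 1 (Section 2.3). This stands, which is why a range is shown.

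A reader might also infer that every incomplete start in the first-dose month or year moves to first dose. It does not: a stop before first dose brings in codes 2 to 4, and the note blocks a start later than the stop. Nor does it follow that incompletely dated cycle 2 events almost never count. That holds for month-known dates and for year-only dates that cross into a new year. The rest still count in the composite, labelled cycle 1.

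**Conclusion.** The point holds in limited form. As written, the rules place code 1 starts in the cycle 1 MDMP whatever their true onset, and keep only about 5 to 7% of true cycle 2 MDMP events dated to the month. These results follow from the table and the cycle length; the 5 to 7% also assumes first-dose dates and event days spread evenly over the calendar. The share of code 1 month-only dates truly in the cycle 1 window does depend on onset: median 25% if uniform, and 36% to 74% under the early-onset patterns tried.

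It would be tempting to conclude that the primary rate is biased upward, or materially wrong. The documents do not support either. The bias can run both ways, no rate of incomplete dates is given, and the net effect cannot be computed. The 2.2 points per subject is 1/45 and would apply to any misclassification. The analysis is descriptive, with no hypothesis test and no formal safety stopping guideline. Severity is minor to moderate. It is worth settling because it concerns the primary endpoint, SAP Section 9.6.1 plans no sensitivity analysis for it, and a choice made after seeing the events would be post hoc.

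**What to change.** Add to SAP Section 5 that start dates imputed under Appendix D are not used for the MDMP flag, nor for time to onset and duration of events of interest.

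For an AE that led to hospitalisation, or a grade 3/4 CRS or NT event, whose start is still incomplete after query, decide membership from the recorded partial date, the stop date, the admission date and the eCRF pre-dose question. If membership is still undetermined, report the primary rate twice: with all such events in, and with all of them out.

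The cost is two SAP sentences and one extra line in the primary table. No new data are needed. The change should be made before lock, and preferably before the next interim review.

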Appendix E Vital Signs and Clinical Monitoring

Table 1. Vital Signs and Clinical Monitoring AMG 103 20190014 VS and Clinical Monitoring

Panel 1

HCP, Subjects & Caregivers (CG)

will receive training in the use

device(s)(CHDs), including the

Subject will wear CHDs during

temperature sensor, BP monitor,

screening to establish baseline VS,

Subject and CG will be trained to

mental status, seizure, jitteriness,

fever, fast or difficult breathing

and other signs and symptoms

on the usual side effects of

blinatumomab (IP) infusion.

IP infusion and response

Subject and CG will be educated

Subject and CG will be educated

to contact HCP for any change or

HCPs will be trained on outpatient

changes/symptoms such as

increased lethargy, change in

and functions of the Current

Health (CH) monitoring

comfort, and eligibility.

recognize clinical

new finding

algorithm

and tablet

Panel 2

- Electronic monitoring including
 - Remote monitoring of vital signs (VS): Respiratory rate (RR), Pulse rate (PR), temperature(T), Blood Pressure(BP), Oxygen saturation(S).
 - Monitoring: Continuous PR, T, and S. intermittent: RR(every 30 secs) and BP(every 3 hrs.)

 - VS algorithm for ALERT to changes in VS as outlined, which are persistent for \geq 10 minutes, with the exception of BP, alert will occur within 1 minute of measurement:
 - Systolic BP \leq 100 mmHg or \geq 20% reduction from
 - Temp ≥ 38.0°C(100.4°F) (Axillary fever scout ≥37.0°C) (99.4°F))
 - S ≤ 92%
 - Neurological algorithm for intervention
 - Any seizure
 - Aphasia (receptive or expressive)
 - Apraxia
 - Altered level of consciousness
 - Impairment of cognitive skills
 - Motor weakness
 - Any change of grade ≥ 3 self-care activities of daily living
 - Any change identified by Patient or caregiver

Panel 3

- Subject proximity (< 1 hr.) to a advanced medical center
- Pre-dose dexamethasone(20mg) will be given prior to initiation of blinatumomab at every cycle.
- Oral dose(s) of steroid available at home, to be taken under HCP direction.
- On day 1 of cycle 1, subject to remain at infusion center for 5 hours after initiating blinatumomab. On day 1 of cycle 2, subject to remain at infusion center for 2 hours after initiating blinatumomab.
 - For cycles 3 and 4, HCP is to follow product information regarding patient monitoring

Either

- Abnormal VS (persistent for \geq 10 minutes). or change in clinical status by patient or CG
- report
- Will generate an immediate alert to HCP
- HCP will contact/communicate with Subject /CG via phone/tablet video monitoring
- HCP response per monitoring algorithm (panel 2)
- HCP will be able to contact Subject/CG for any concerns in absence of an alert
- Subject /CG will be able to contact HCP, or Emergency services directly as needed
- BP = blood pressure; HCP = healthcare professional; IP = Investigational product

- Establishment of Subject baseline during screening
- HCP may order more frequent VS as needed.
- - baseline (established in screening)

 - $R \leq 10 \text{ or} \geq 25$
 - $PR \leq 60 \text{ or } \geq 150$
